3.2 Secondary Outcome Measures (Arm 2)

- 1. [For Secondary Objective 1] Non-compartmental PK parameters:
 - a. RDV AUC
 - b. RDV t_{1/2}
 - c. GS-441524 Ctrough

- 2. [For Secondary Objective 2] Clinical and laboratory safety outcomes:
 - a. Renal adverse events of any grade through 7 days post-last infusion
 - b. Hepatic adverse events of any grade through 7 days post-last infusion
 - c. Hematologic events of any grade through 7 days post-last infusion
 - d. Adverse events through 4 weeks post-last infusion:
 - i. Grade 3 or higher adverse events
 - ii. Serious adverse events
 - iii. Grade 3 or higher adverse events assessed as related to RDV by the CMC

Note: Additional non-compartmental PK parameters, described in Table 2 of the PK SAP, will also be summarized for Arm 2 as part of the Primary Analysis Report for RDV, GS-441524, and/or GS-704277 (data permitting).

4 General Considerations

The derivation of PK parameters will be performed by the IMPAACT 2032 protocol pharmacologist(s), as described in the PK SAP. The statistical summaries to be prepared by the statisticians are described in this Primary SAP.

For primary and secondary PK analyses, the PK Evaluable analysis set will be used. This analysis set will include women who have at least 3 out of 4 of the pre-dose through 3 hours postend-of-infusion (post-EOI) intensive PK samples, either the 5 hours post-EOI or the 7 hours post-EOI intensive PK sample, and either the pre-dose or 23 hour post-EOI samples collected. In addition to these minimum requirements for sample collections, drug concentrations will also be reviewed once available to further assess whether the participant is PK evaluable. PK evaluability will be determined by the protocol pharmacologists and CMC on a case-by-case basis. If a participant is deemed unevaluable for PK, the CMC will determine how to proceed with replacement. For primary and secondary safety analyses, the Safety analysis set will be used. This analysis set includes all women who receive any amount of RDV.

Continuous variables will be summarized by N, N missing, mean, standard deviation, and quantiles of minimum, 25th percentile, median, 75th percentile, and maximum. Categorical variables will be summarized by N (%) in each category, excluding the missing category in the denominator. PK parameters will be also summarized using geometric and arithmetic means, % CVs, and 90% CIs. The 90% CI for the arithmetic mean will be calculated on the log scale using the modified Cox approach (Olsson, 2017). The 90% CI for the geometric mean will be calculated using the t distribution on the log scale.

The Pre-infusion Period will refer to the period 48 hours before initiation of RDV infusions for COVID-19. If there is more than one record before the start of infusions, the last one before it (proximal) will be used, unless otherwise noted. The Infusion Period begins at the start of the first infusion and continues through the day of the last infusion, and the Safety Follow-up Period begins from the first day after the last RDV infusion and continues for 4-weeks after the last RDV infusion. This period is divided into 3 data collection time points: 48-Hours, 7-Days, and 4-Weeks

Post-Last Infusion. For Arm 1, the Delivery Period is defined as the period from onset of labor or start of Cesarean section through 24 hours after delivery.

Because women of any gestational age can be enrolled in the study and each trimester of pregnancy provides differing physiological changes that can affect bioavailability of drugs, primary analyses will also be presented by trimester for Arm 1.

5 Estimands and Estimation

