9 STATISTICAL CONSIDERATIONS

9.1 General Design Issues

This is a Phase IV prospective, open label, non-randomized opportunistic study to describe the PK properties and safety of RDV administered intravenously as part of clinical care among hospitalized pregnant and non-pregnant women with COVID-19. This study is comprised of two arms specific to the study population. The first arm will include pregnant women, while the second arm will include non-pregnant women of childbearing potential. PK sampling will be performed during the RDV infusions and women will be followed for safety for four weeks after the last infusion; Arm 1 women who are still pregnant at that time will continue to be followed for safety at delivery.

The target sample size is 20 PK-evaluable women for each arm. A participant's PK data will be deemed unevaluable by a protocol pharmacologist for a specific analysis if they do not have adequate PK evaluations to determine the PK parameter of interest for that analysis (see Sections 9.6 and 10.2 for details). If a participant is deemed unevaluable for PK, the CMC will determine how to proceed with replacement. All women who receive any amount of RDV after enrollment will be evaluable for the safety analyses.

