The intracellular concentrations of GS-443902 at each timepoint and in each arm will be summarized using descriptive statistics and compared between pregnant and non-pregnant women using the GMR with a 90% CI. Individual-level concentrations over time will also be visualized using spaghetti plots and compared within individual.

The RDV free fraction from *ex vivo* experiments will be summarized using descriptive statistics for pregnant and non-pregnant women, as will the unbound RDV concentrations (calculated as follows: total concentration x free fraction) and the Albumin and AAG concentrations.

For lactating women meeting breast milk collection criteria, the number and percentage of women with detectable maternal breast milk concentrations for RDV and GS-441524, and the breast milk/plasma ratios, will be calculated and summarized using descriptive statistics. Timing of breast milk and plasma sample collection since EOI will also be summarized.

All analyses will include all participants with evaluable data for that analysis (see Section 10.2 for the definition of PK-unevaluable. For the safety analyses, a participant will only be deemed unevaluable if she does not receive any amount of RDV.

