5.1 Primary Estimands

5.1.1 First Primary Estimand

Primary Objective 1: To describe the pharmacokinetics of RDV and its metabolite, GS- 441524, after administration to pregnant women as part of clinical care		
Estimand description Geometric mean of PK parameter (RDV AUC/RDV t _{1/2} / GS-441524 C _{trough}) ir hospitalized pregnant woman, who tolerated at least 3 RDV infusions for the treatment of COVID-19.		
Treatment Remdesivir (RDV)		
Target population	Analysis set	
Hospitalized pregnant women who received and	PK-evaluable women	
tolerated at least 3 RDV infusions for treatment	(PK Evaluable analysis set)	
of COVID-19	NOTE: Women will be considered PK evaluable if they have at least 3 out of 4 of the pre-dose through 3 hours post-end-of- infusion (post-EOI) intensive PK samples, either the 5 hours post-EOI or the 7 hours post-EOI intensive PK sample, and either the pre-dose or 23 hour post-EOI samples collected. In addition to these minimum requirements for sample collections, drug concentrations will also be reviewed once available to further assess whether the participant is PK evaluable. For t _{1/2} , women will be PK evaluable if they have the additional requirement of 3 consecutive declining points in the curve.	
Variable(s)	Outcome measure(s)	
1. RDV concentration in plasma	Non-compartmental PK parameters:	
2. RDV concentration in plasma	1. RDV area under the plasma	
3. GS-441524 concentration in plasma	concentration-time curve (AUC) 2. RDV half-life (t _{1/2})	
	3. GS-441524 trough concentration	
	(Ctrough)	
Handling of intercurrent events	Handling of missing data	
The following intercurrent events are relevant to	Only participants who are deemed PK	
the estimand:	evaluable will be included in the final	
1. Onset of labor	analysis (i.e., missing observations due to	
2. Discontinue treatment for toxicity or non-toxicity reasons	missing or inadequate sampling are considered missing completely at random).	
3. Maternal death		

These intercurrent events will be addressed using a principal stratum approach.	Participants who do not undergo intensive PK sampling will not be included in the final analysis (i.e., missing observations due to drop out prior to intensive PK sampling are considered missing completely at random).
	Given the descriptive nature of the primary analyses, there are no planned supplementary or sensitivity analyses.
Population-level summary measure	Analysis approach

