5.2 Secondary Estimands

5.2.1 First Secondary Estimand

Secondary Objective 1: To describe the pharmacokinetics of RDV and its metabolite, GS-441524, after administration to non-pregnant women of childbearing potential as part of clinical care			
Estimand description	Geometric mean of PK parameter (RDV AUC/RDV t _{1/2} / GS-441524 C _{trough}) in hospitalized non-pregnant woman of childbearing potential, who tolerated at least 3 RDV infusions for the treatment of COVID-19.		
Treatment	Remdesivir (RDV)		
Target population	ו	Analysis set	
Hospitalized non-pregnant women of childbearing potential who received and tolerated at least 3 RDV infusions for the treatment of COVID-19		PK-evaluable women (PK Evaluable analysis set) NOTE: Women will be considered PK evaluable if they have at least 3 out of 4 of	

	the pre-dose through 3 hours post-end-of- infusion (post-EOI) intensive PK samples, either the 5 hours post-EOI or the 7 hours post-EOI intensive PK sample, and either the pre-dose or 23 hour post-EOI samples collected. In addition to these minimum requirements for sample collections, drug concentrations will also be reviewed once available to further assess whether the participant is PK evaluable. For t _{1/2} , women will be PK evaluable if they have the additional requirement of 3 consecutive declining points in the curve.
Variable(s)	Outcome measure(s)
 RDV concentration in plasma RDV concentration in plasma GS-441524 concentration in plasma 	 Non-compartmental PK parameters: 1. RDV area under the plasma concentration-time curve (AUC) 2. RDV half-life (t_{1/2}) 3. GS-441524 trough concentration (C_{trough})
Handling of intercurrent events	Handling of missing data
 The following intercurrent events are relevant to the estimand: 1. Discontinue treatment for toxicity or non-toxicity reasons 2. Death 	Only participants who are deemed PK evaluable will be included in the final analysis (i.e., missing observations due to missing or inadequate sampling are considered missing completely at random).
These intercurrent events will be addressed using a principal stratum approach.	Participants who do not undergo intensive PK sampling will not be included in the final analysis (i.e., missing observations due to drop out prior to intensive PK sampling are considered missing completely at random).
	Given the descriptive nature of the primary analyses, there are no planned supplementary or sensitivity analyses.
Population-level summary measure	Analysis approach

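### The composite PK sampling rule can drop women with a valid intensive-day GS-441524 trough from Ctrough, a parameter that needs only that one sample

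*SAP*

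**What the plan says.** SAP Section 4 names one set for the three primary PK outcomes in Arm 1 and the three secondary ones in Arm 2: "For primary and secondary PK analyses, the PK Evaluable analysis set will be used". The sampling conditions are cumulative. The early part reads "This analysis set will include women who have at least 3 out of 4 of the pre-dose through 3 hours" after end of infusion (EOI), and the later part "either the 5 hours post-EOI or the 7 hours post-EOI intensive PK sample, and either the pre-dose or 23 hour post-EOI samples collected". Concentrations are then reviewed in addition to these minimum requirements, and the pharmacologists and the Clinical Management Committee (CMC) decide case by case.

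SAP 5.1.1 and 5.2.1 repeat the rule and close the analysis to everyone else: "Only participants who are deemed PK evaluable will be included in the final analysis". The only parameter-specific element is for RDV half-life, which has the "additional requirement of 3 consecutive declining points in the curve". Exclusions for missing or inadequate sampling are treated as missing completely at random, and no sensitivity analysis is planned.

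The protocol speaks in two ways. Section 9.1 has a pharmacologist deem data unevaluable "for a specific analysis if they do not have adequate PK evaluations to determine the PK parameter of interest for that analysis", and Section 9.6 says "All analyses will include all participants with evaluable data for that analysis". Both sections refer to Section 10.2 for the definition, and 10.2 contains the same composite rule as the SAP, again with case-by-case assessment of incomplete profiles.

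**The concern.** Ctrough is one concentration. It does not depend on the RDV profile from end of infusion to 7 h. A woman with pre-dose, EOI, 0.75, 1.5, 3 and 23 h samples has a measured trough, yet fails the minimum rule because both the 5 h and 7 h samples are missing. The test in protocol 9.1 would keep her for Ctrough; the composite rule would not.

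The reverse case concerns RDV AUC. A woman with a good profile from EOI to 5 h or 7 h, but neither a pre-dose nor a 23 h sample, fails although those two samples carry almost no RDV.

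At stake is precision on a primary outcome in an arm of about 20, whose primary results are also to be shown by trimester. A second issue is clarity: a reader cannot tell from the two documents which women belong in the Ctrough summary.

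**Working it through.** **1. The plan's own figures.** Enrolment limit (protocol 9.4.2): 20 / (1 − 0.20) = 25 per arm, as stated. Modified Cox 90% limits (protocol Table 8, SAP Table 1): exp(±t·√(s²/n + s⁴/(2(n−1)))), with s² = ln(1 + CV²) and t the 95th percentile on n−1 degrees of freedom. For CV 0.3, s² = 0.0862. At n = 20, t = 1.729 and the root is 0.0671, giving 89.0% to 112.3%, width 23.3%. This matches, as do all nine cells of the table.

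**2. Which sample patterns fail.** Protocol Table 4 lists eight samples, so there are 2⁸ = 256 collected/missing patterns, of which 192 include a pre-dose or 23 h sample. Table 4 shows five samples from pre-dose to 3 h, whereas the rule says three out of four, so two readings are possible.
- Four post-dose samples counted (EOI to 3 h): 5 × 3 × 3 = 45 patterns pass, so 192 − 45 = 147 patterns with a trough fail.
- All five counted: with pre-dose present, 11 early patterns × 2 for the 23 h sample = 22; with pre-dose absent and 23 h present, 5; together 27, times 3 for 5 h/7 h, gives 81. So 192 − 81 = 111 fail.

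**3. Expected numbers.** The documents give no per-sample missing rate, so a rate q, independent across samples, is assumed. Either the pre-dose or the 23 h sample is counted as a trough, since neither document says which one defines Ctrough. With p = 1 − q:
- P(trough) = 1 − q².
- P(evaluable, four-sample reading) = (p⁴ + 4p³q)(1 − q²)². At q = 0.20: 0.8192 × 0.9216 = 0.755.
- Troughs lost per 25 at q = 0.20: 25 × (0.960 − 0.755) = 5.1.
- RDV AUC lost (at least three of EOI to 3 h, plus 5 h or 7 h, but neither pre-dose nor 23 h) = (p⁴ + 4p³q)(1 − q²)q². At q = 0.20: 0.8192 × 0.96 × 0.04 = 0.0315, or 0.79 per 25.

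| Assumed q | Troughs lost per 25, five-sample reading | Troughs lost per 25, four-sample reading | RDV AUCs lost per 25 |
|---|---|---|---|
| 5% | 0.09 | 0.41 | 0.06 |
| 10% | 0.45 | 1.53 | 0.23 |
| 15% | 1.14 | 3.17 | 0.49 |
| 20% | 2.18 | 5.13 | 0.79 |

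If only one of the two samples defines Ctrough, the top figure becomes 25 × 0.8 × (1 − 0.8192 × 0.96) = 4.3.

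**4. Effect on precision (CV 0.3).** The upper bound takes all five anticipated unevaluable women as having a usable trough.
- Modified Cox, arithmetic mean: width 23.3% at n = 20, 22.1% at n = 22, 20.6% at n = 25. At CV 0.4 it goes from 31.1% to 27.5% (n = 20 to 25).
- t interval for the geometric mean, the SAP's estimand, exp(±t·s/√n) with s = 0.2936: at n = 20, exp(±0.1135), width 22.7%; at n = 25, exp(±0.1005), width 20.1%.

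**5. What the late samples add to RDV AUC.** Under a mono-exponential model, the share of AUC beyond time t after EOI is [(1 − e^(−kT))/(kT)]·e^(−kt), with k = ln 2 / half-life. For half-lives of 0.82–1.09 h (quartiles in protocol Table 1) and infusions of T = 0.5 or 2 h (protocol 5.2), 0.7–3.6% lies beyond 5 h, 0.1–1.0% beyond 7 h, and under 0.0001% beyond 23 h.

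**The case against.** The strongest reply is that the SAP follows the protocol. Sections 9.1 and 9.6 both point to 10.2, and the SAP copies 10.2. This stands. A reader might infer that the SAP overrides the protocol, but the tension is inside the protocol, and a change to the SAP alone would leave 10.2 unresolved.

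Second, case-by-case review could retain such women, so it cannot be said that their data will be discarded. This stands in part: the SAP frames the review as additional to minimum requirements, which suggests that it removes women rather than restores them.

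Third, the late samples are not irrelevant to RDV AUC under the linear trapezoidal method (protocol 10.4.1). If the AUC runs over the dosing interval, which the documents do not fix, a trapezoid from 7 h to 23 h contributes. At a half-life of 0.89 h and a 30-minute infusion, the 7 h level is 0.43% of the EOI level, so that trapezoid is 16 × 0.0043 / 2 = 0.034 against a total of about 1.55 (in EOI level × hours), or about 2%. The sample is used, but for little.

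Fourth, n = 25 cannot be expected: some unevaluable women may have no intensive-day samples, for example those who never start RDV (protocol 4.7). Replacement and an expandable enrolment limit protect the target of 20. Both points stand.

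Fifth, a common set for descriptive summaries is defensible, and the separate PK SAP, which was not available, may define Ctrough and parameter-level rules. However, the Primary SAP defines the analysis set, and it already departs from a common set for half-life.

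**Conclusion.** The point holds for Ctrough. Under the stated minimum rule, a valid intensive-day trough can be excluded for lack of samples that the parameter does not need, while protocol 9.1 and 9.6 would judge it on its own. For RDV AUC the effect is minor, under about one woman per 25.

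The size is modest: roughly 0.1 to 5 troughs per 25 enrolled, resting on an assumed, independent 5–20% missing rate, on the reading of the three-out-of-four condition, and on counting either sample as a trough. The move from 23.3% to 20.6% in interval width is an upper bound.

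Two stronger readings are not supported. A reader might infer that the rule selectively removes sicker or earlier-discharged women and so biases the results; neither document gives a figure or statement on who misses these samples. Nor is any stated sample size, precision or power figure wrong: the target of 20 and the limit of 25 are unaffected.

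**What to change.** - In SAP 4, 5.1.1 and 5.2.1, define evaluability per parameter. Ctrough should require only the designated intensive-day trough sample, whatever else is missing. RDV AUC and half-life keep conditions suited to the RDV profile, with the existing extra condition for half-life.
- State whether Ctrough is the pre-dose or the 23 h value; the current condition, "either the pre-dose or 23 hour post-EOI samples collected", leaves this open. Exclude sparse-day troughs: the single draws on infusion days 2–5 aim for pre-infusion times (protocol 6.4.2), GS-441524 takes 4 days to reach steady state (protocol 1.2), and the estimand concerns women who tolerated at least three infusions.
- Say which samples the three-out-of-four condition counts.
- Keep the composite rule for counting toward 20 per arm and for replacement, and say in protocol 10.2 that this is its role, so that it agrees with 9.1 and 9.6.
- Show n for each parameter. SAP 4 already asks for N and N missing; these should now be read against parameter-specific sets.

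The cost is wording only, with samples already collected. The downside is an n that differs between parameters, and naming a single trough sample gives up women who have only the other one.

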5.1 Primary Estimands

5.1.1 First Primary Estimand

Primary Objective 1: To describe the pharmacokinetics of RDV and its metabolite, GS- 441524, after administration to pregnant women as part of clinical care		
Estimand description Geometric mean of PK parameter (RDV AUC/RDV t _{1/2} / GS-441524 C _{trough}) ir hospitalized pregnant woman, who tolerated at least 3 RDV infusions for the treatment of COVID-19.		
Treatment Remdesivir (RDV)		
Target population	Analysis set	
Hospitalized pregnant women who received and	PK-evaluable women	
tolerated at least 3 RDV infusions for treatment	(PK Evaluable analysis set)	
of COVID-19	NOTE: Women will be considered PK evaluable if they have at least 3 out of 4 of the pre-dose through 3 hours post-end-of- infusion (post-EOI) intensive PK samples, either the 5 hours post-EOI or the 7 hours post-EOI intensive PK sample, and either the pre-dose or 23 hour post-EOI samples collected. In addition to these minimum requirements for sample collections, drug concentrations will also be reviewed once available to further assess whether the participant is PK evaluable. For t _{1/2} , women will be PK evaluable if they have the additional requirement of 3 consecutive declining points in the curve.	
Variable(s)	Outcome measure(s)	
1. RDV concentration in plasma	Non-compartmental PK parameters:	
2. RDV concentration in plasma	1. RDV area under the plasma	
3. GS-441524 concentration in plasma	concentration-time curve (AUC) 2. RDV half-life (t _{1/2})	
	3. GS-441524 trough concentration	
	(Ctrough)	
Handling of intercurrent events	Handling of missing data	
The following intercurrent events are relevant to	Only participants who are deemed PK	
the estimand:	evaluable will be included in the final	
1. Onset of labor	analysis (i.e., missing observations due to	
2. Discontinue treatment for toxicity or non-toxicity reasons	missing or inadequate sampling are considered missing completely at random).	
3. Maternal death		

These intercurrent events will be addressed using a principal stratum approach.	Participants who do not undergo intensive PK sampling will not be included in the final analysis (i.e., missing observations due to drop out prior to intensive PK sampling are considered missing completely at random).
	Given the descriptive nature of the primary analyses, there are no planned supplementary or sensitivity analyses.
Population-level summary measure	Analysis approach
Geometric mean of PK parameter (RDV AUC/RDV t _{1/2} / GS-441524 C _{trough}) in hospitalized pregnant women	Geometric mean of PK parameter (RDV AUC/RDV t _{1/2} / GS-441524 C _{trough}), bounded by a 90% CI calculated using the t
	distribution on the log scale

5.1.2 Second Primary Estimand

Primary Objective 2: To describe the clinical and laboratory safety outcomes through 4 weeks post-infusion and during delivery in pregnant women receiving RDV as part of				
clinical care. Estimand description	(A) Probability of a pregnant woman, who received any amount of RDV while hospitalized for the treatment of COVID-19,* having at least one adverse event (maternal renal/hepatic/hematologic of any grade) or death through 7 days post-last infusion.			
	(B) Probability of a pregnant woman, who received any amount of RDV while hospitalized for the treatment of COVID-19,* having at least one adverse event (maternal Grade 3 or higher/serious/maternal Grade 3 or higher assessed as related by the CMC) or death through 4 weeks post-last infusion and at delivery.			
	(C) Probability of a pregnant woman, who received any amount of RDV while hospitalized for the treatment of COVID-19,* having a labor/delivery outcome (pregnancy loss/congenital anomalies/preterm birth < 37 weeks/preterm birth < 34 weeks/SGA), pregnancy loss, or death.			
	*NOTE: This study design is opportunistic in that it enrolls women who may have already received at least one infusion of RDV. Because participants can be enrolled any time prior to the 4 th infusion, the study population will potentially not include women who started RDV and discontinued it prior to the 4 th infusion due to toxicity, intolerance, virologic failure, or any other reason. Consequently, the results may be overly optimistic.			
Treatment	Remdesivir (RDV)			
Target population		Analysis set		
	n who received any amount of talized for treatment of	Pregnant women who received any amount of RDV (Safety analysis set)		
that it enrolls wo	dy design is opportunistic in men who may have already one infusion of RDV.			

Because participants can be enrolled any time	
prior to the 4 th infusion, the study population	
will potentially not include women who started	
RDV and discontinued it prior to the 4 th	
infusion due to toxicity, intolerance, virologic	
failure, or any other reason. Consequently, the	
results may be overly optimistic.	
Variable(s)	Outcome measure(s)
(A) Occurrence of each of the following	Outcome measures as defined by the
through 7 days post-last infusion: 1. Maternal renal adverse events of any	variables
grade	
2. Maternal hepatic adverse events of	
any grade	
3. Maternal hematologic adverse events	
of any grade	
(B) Occurrence of each of the following	
through 4 weeks post-last infusion and during	
delivery:	
1. Maternal Grade 3 or higher adverse events	
2. Serious adverse events	
3. Maternal Grade 3 or higher adverse	
events assessed as related to RDV by	
the CMC	
(C) Occurrence of each of the following	
labor/delivery outcomes*:	
1. Pregnancy loss	
 Congenital anomalies Preterm birth < 37 weeks 	
4. Preterm birth < 34 weeks	
5. Small for gestational age (SGA) (< 10 th	
percentile for gestational age)	
······································	
*For multiple births, the "worst" outcome within	
the sibling set will be used.	
Handling of intercurrent events	Handling of missing data
The following intercurrent events are relevant	Missing data will be handled using an
to the estimand:	"available case" approach. Outcome
 Maternal death Terminal fetus/infant event 	measures for participants who discontinue
	follow-up before the time point of interest (i.e., 7 days post-last infusion/4 weeks post-
Maternal death will be addressed using a	last infusion and delivery) and did not have
composite event approach.	an event of interest will be missing (i.e.,
	these participants will not be included in the
Terminal fetus/infant event will be addressed	denominator).
as a composite event for pregnancy loss. A	
principal stratum approach will be used for	Labor/delivery outcome measures for
congenital anomalies, preterm birth, and SGA.	participants who discontinued follow-up
	before delivery will not be included (i.e.,
	missing observations that would be relevant

A supplementary analysis that applies a principal stratum approach for maternal death will be used for relevant outcome measures.	to the variable are considered missing completely at random). As a sensitivity analysis, we will use multiple imputation over a range of potential probabilities, including "best case" (i.e., probability of event = 0) and "worst case" (i.e., probability of event = 1) scenarios.
Population-level summary measure	Analysis approach
(A) Probability of a pregnant woman, who received any amount of RDV for the treatment of COVID-19, having at least one adverse event (maternal renal/hepatic/hematologic of any grade) through 7 days post last infusion	(A) Proportion of participants with at least one adverse event (maternal renal/hepatic/hematologic of any grade) through 7 days post last infusion, bounded by an exact 95% CI
(B) Probability of a pregnant woman, who received any amount of RDV for the treatment of COVID-19, having at least one adverse event (maternal Grade 3 or higher/serious/maternal Grade 3 or higher assessed as related by the CMC) through 4 weeks post last infusion and at delivery	 (B) Proportion of participants with at least one adverse event (maternal Grade 3 or higher/serious/maternal Grade 3 or higher assessed as related by the CMC) through 4 weeks post last infusion, bounded by an exact 95% Cl
(C) Probability of a pregnant woman, who received any amount of RDV for the treatment of COVID-19, having at least one labor/delivery outcome (pregnancy loss/congenital anomalies/preterm birth < 37 weeks/preterm birth < 34 weeks/SGA)	(C) Proportion of participants with at least one labor/delivery outcome (pregnancy loss/congenital anomalies/preterm birth < 37 weeks/preterm birth < 34 weeks/SGA), bounded by an exact 95% Cl

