2.5 Formal Interim Monitoring

No formal interim analyses were planned or specified in the study protocol. The plans for study monitoring are described in Section 9.5 of the protocol (Version 2.0).

3 Outcome Measures

3.1 **Primary Outcome Measures (Arm 1)**

- 1. [For Primary Objective 1] Non-compartmental PK parameters:
 - a. RDV area under the plasma concentration-time curve (AUC)
 - b. RDV half-life (t_{1/2})
 - c. GS-441524 trough concentration (Ctrough)
- 2. [For Primary Objective 2] Clinical and laboratory safety outcomes:
 - a. Maternal renal adverse events of any grade through 7 days post-last infusion
 - b. Maternal hepatic adverse events of any grade through 7 days post-last infusion
 - c. Maternal hematologic events of any grade through 7 days post-last infusion
 - d. Adverse events through 4 weeks post-last infusion and during delivery:
 - i. Maternal Grade 3 or higher adverse events
 - ii. Serious adverse events
 - iii. Maternal Grade 3 or higher adverse events assessed as related to RDV by the CMC
 - e. Labor/delivery outcomes:
 - i. Pregnancy loss
 - ii. Congenital anomalies
 - iii. Preterm birth (< 37 weeks, < 34 weeks)
 - iv. Small for gestational age (SGA) (< 10th percentile for gestational age)
 - f. Newborn physical exam:
 - i. Birth weight
 - ii. Length
 - iii. Head circumference

Note: Additional non-compartmental PK parameters, described in Table 2 of the PK SAP, will also be summarized for Arm 1 as part of the Primary Analysis Report for RDV, GS-441524, and/or GS-704277 (data permitting).

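### SAP 5.1.2 and 5.2.2 count a death the CMC calls unrelated in the CMC-related rate; 5.1.2 also conflicts on pregnancy loss and omits delivery from an analysis row

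*SAP*

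**What the plan says.** SAP 5.1.2 (Arm 1, second primary estimand) sets out three groups of safety outcomes in a table.

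- **Description row.** Death is added to each group. (A) covers "maternal renal/hepatic/hematologic of any grade) or death through 7 days post-last infusion". (B) ends "maternal Grade 3 or higher assessed as related by the CMC) or death through 4 weeks post-last infusion and at delivery". (C) is "having a labor/delivery outcome (pregnancy loss/congenital anomalies/preterm birth < 37 weeks/preterm birth < 34 weeks/SGA), pregnancy loss, or death".
- **Variables row.** Each outcome is listed separately, without death. (B) runs through 4 weeks and during delivery. The outcome-measure row reads "Outcome measures as defined by the" variables.
- **Handling of intercurrent events.** "Maternal death will be addressed using a" composite event approach, and no outcome is exempted. A terminal fetus/infant event is a composite for pregnancy loss only; a principal stratum is used for "congenital anomalies, preterm birth, and SGA". A supplementary principal-stratum analysis for maternal death is promised for relevant outcomes, which are not named.
- **Summary and analysis rows.** Neither mentions death. Summary row (B) includes delivery; analysis row (B) stops at 4 weeks.

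SAP 3.1 lists the Arm 1 outcome as "Maternal Grade 3 or higher adverse events assessed as related to RDV by the CMC", under a heading that covers 4 weeks and delivery. SAP 3.2 lists the Arm 2 outcome as "Grade 3 or higher adverse events assessed as related to RDV by the CMC". Neither includes death. SAP 5.2.2 repeats the pattern on death for (A) and (B). Protocol Section 8 has the CMC review every relatedness assessment and uses its classification for analysis.

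**The concern.** The CMC-related outcome exists to separate events with a reasonable possibility of a link to remdesivir from everything else that happens to women hospitalized with COVID-19. A composite with death from any cause undoes that separation, and the resulting rate is not the outcome listed in SAP 3.1 and 3.2. For Arm 1 it is a primary safety outcome, and SAP 1.1 says results for these outcomes will be posted on ClinicalTrials.gov.

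The other two conflicts need no maternal death. Under description (C) a pregnancy loss counts as a preterm birth, an anomaly and a small-for-gestational-age infant; under the handling row it does not. Analysis row (B), taken literally, discards Grade 3 or higher, serious and related events at any delivery later than 4 weeks after the last infusion. Women of any gestational age are eligible (Protocol 4.1.2), so late deliveries are to be expected.

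**Working it through.** **Rows of SAP 5.1.2 side by side, with SAP 3.1**

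| Row | Death | Pregnancy loss added to other (C) outcomes | Delivery in (B) |
|---|---|---|---|
| Description | counted in A, B, C | yes | yes |
| Variables | not mentioned | no | yes |
| Handling | composite, none exempt | no: principal stratum for three outcomes | not addressed |
| Summary | not mentioned | no | yes |
| Analysis | not mentioned | no | no |
| SAP 3.1 | not mentioned | no | yes |

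The variables row takes the occurrence of each outcome, so the slash-separated lists are separate outcomes. For the CMC-related one, the description and handling rows then give: related Grade 3 or higher event, or any death.

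**Interval method.** SAP 2.4 uses Clopper-Pearson limits. For x events in n women, the lower limit is the 0.025 quantile of Beta(x, n-x+1) and the upper limit is the 0.975 quantile of Beta(x+1, n-x). For x = 0 the lower limit is 0 and the upper limit is 1 - 0.025^(1/n).

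**The plan's own figure.** For 4/20 this gives 5.73% to 43.66%, which rounds to the stated 6%-44%. All 18 rows of SAP Table 2 reproduce. No stated figure is wrong.

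**Illustrations.** All event counts are assumed; the documents give none.

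1. CMC-related outcome, no related event, one death classed as unrelated.
   - n = 20: description and handling rows 1/20 = 5% (0.1-24.9%); death not counted and the woman kept 0/20 = 0% (0-16.8%, from 1 - 0.025^(1/20)).
   - n = 25, the initial enrollment limit per arm (Protocol 9.4.2): 1/25 = 4% (0.1-20.4%) against 0/25 (0-13.7%).
   - Each such death adds 1/20 = 5 points or 1/25 = 4 points.
2. Preterm birth, 20 pregnancies, one pregnancy loss, two preterm births.
   - Description (C): (2 + 1)/20 = 15.0% (3.2-37.9%).
   - Handling row, if principal stratum means excluding the loss: 2/(20 - 1) = 2/19 = 10.5% (1.3-33.1%).
3. Grade 3 or higher events, six of 20 women affected, two of them only at a delivery after 4 weeks.
   - With delivery: 6/20 = 30% (12-54%).
   - By analysis row (B): (6 - 2)/20 = 4/20 = 20% (6-44%). Both intervals appear in SAP Table 2.

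**The case against.** **Silence is not contradiction.** The two rows of 5.1.2 that speak to death agree with each other, and no row says death is not an event. The variable, summary and analysis rows may be shorthand, to be read with the handling row. This is a fair reading, but it does not rescue the CMC-related outcome: on that reading an unrelated death certainly enters the related rate.

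**The composite looks deliberate.** It is paired with a supplementary principal-stratum analysis for maternal death. This stands. A reader might infer that death must come out of every primary safety outcome. The documents do not support that. Counting death with the organ-class outcomes is a trade-off, because an event-only rate may understate risk when a woman dies early.

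**A third denominator.** A reader might also infer that a woman who dies is dropped as missing, giving 0/19. That is strained: it requires setting aside the handling row and treating death as discontinued follow-up.

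**Delivery is a one-row slip.** Probably so, since the description, variable and summary rows and SAP 3.1 all include it. But the analysis row is the one that specifies the computed proportion, so it should be corrected.

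**The coding may already be settled.** SAP 1.1 places coding descriptions in the Analysis Implementation Plan, which is not among the documents. It may resolve all of this, but the SAP is where the estimand is stated.

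**Conclusion.** Three defects stand. First, as the estimand is described and death is handled, an unrelated death counts in the CMC-related rate, against SAP 3.1 and 3.2 and Protocol Section 8. Second, description (C) and the handling row disagree on pregnancy loss. Third, Arm 1 analysis row (B) omits delivery. The first also applies to Arm 2 through 5.2.2.

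The size is conditional. The death effect is 5 points per death in 20 women, or 4 points in 25, and needs a death in the window in a woman without the qualifying event. Among the 67 pregnant women in the compassionate-use series in Protocol 1.2 there was no death, so the effect may not arise. The 15.0% against 10.5% contrast assumes that principal stratum means exclusion, which 5.1.2 does not say. Whether a death would already count as Grade 3 or higher or as serious depends on a grading table and a definition that the documents cite but do not reproduce, so the effect on those two rates cannot be settled here.

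A reader might infer that the trial's conclusions or monitoring are compromised. They are not: the study is descriptive, with no hypothesis (SAP 2.2) and no safety stopping rule (Protocol 9.5.1). The newborn measurements in SAP 5.1.3 already use a principal stratum and are unaffected. The wording should be corrected before the Primary Analysis Report is finalized.

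**What to change.** In SAP 5.1.2, and in 5.2.2 for (A) and (B):

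1. For the CMC-related outcome, count a death only if the CMC classes it as related. Report all-cause death on its own line.
2. In description (C), delete the added pregnancy loss for anomalies, preterm birth and small for gestational age, so that it matches the handling row. Report pregnancy loss as its own outcome.
3. Add delivery to Arm 1 analysis row (B).
4. For the other outcomes, make the description, variable, summary and analysis rows agree on death. If the composite stays primary, label those rates as event or death, and also report the event-only proportion with women who die kept in the denominator.
5. Name the outcomes that the supplementary principal-stratum analysis covers.
6. Editorial, in 5.2.2: remove the reference to delivery from description (B), and change maternal death to death.

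The cost is SAP wording and one or two extra reported lines. Serious events, CMC relatedness and pregnancy outcomes are already collected (Protocol 7.2.2, Section 8 and Table 6), so no new data are needed.
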